3. STUDY DESIGN

3.1. Overall Design

This is a Phase 2, open-label, dose-ranging study designed to provide safety, efficacy, and PK of tildacerfont, as well as the impact of tildacerfont on adrenal androgens and GC requirements in participants with classic CAH.

Three staggered cohorts (Cohorts 1-3) are planned to investigate QD dosing over 12 weeks of treatment, with an additional optional Cohort 1a, dependent on accumulating safety data. The study is expected to enroll approximately 20 children across the first 3 cohorts (i.e., Cohorts 1, 2, and 3), 10 in the 11-to 17-year age group and 10 in the 2-to 10- year age group. If the optional Cohort 1a is initiated (up to 5 participants), however, Cohorts 1 to 3 may enroll up to 25 children total, 15 in the 11-to 17-year-old age group and 10 in the 2-to 10-year-old age group.

Up to an additional six cohorts (Cohorts 4-9) are planned to investigate BID dosing over 4 weeks of treatment. The study will also enroll up to approximately 15 adults aged ≥ 18 years across Cohorts 4 and 5; and up to approximately 30 children across 4 additional cohorts [up to 15 in the 11- to 17-year age group (Cohorts 6 and 8) and up to 15 in the 2- to 10-year age group (Cohorts 7 and 9)].

If all possible doses are studied, total sample size of this study may be up to approximately 55 children and 15 adults ([Table 1](#)).

Participants enter the study on their current GC regimen (note: dexamethasone is excluded). In Cohorts 1-3, GC dose may be adjusted based on A4 levels at specified weeks and at any visit during the extension. In Cohorts 4-9, there will be no GC adjustment during the 4-week study period, but GC doses can be adjusted for those who participate in the optional extension at Week 4 and any subsequent visit. For further details refer to [Section 5.3.1.2](#).

Cohorts 1 to 3:

Cohorts 1, 1a (if indicated), and 2 will include children ages 11- to 17-years old (up to approximately 5 participants in each cohort), and Cohort 3 (up to approximately 10 participants) will include children ages 2- to 10-years old.

For these cohorts, the study will last approximately 18 weeks including a 2-week Screening Period, a 12-week Treatment Period and a Safety Follow-up visit 30 days after the last dose of study drug (during the Treatment Period). Participants may continue in an extension period upon completion of the 12-week Treatment Period. If participants enroll in the extension study after the 12-week Treatment Period, the Safety Follow-up Visit will occur 30 days after the last dose in the extension.

Dosing will begin in Cohort 1 with participants 11- to 17- years of age dosing at the adult equivalent of 50 mg QD. Cohort 2 will continue in the same 11– to 17-year-old age group but dosing at 200 mg QD. Cohort 3 will enroll participants 2-to 10-years of age but dose no higher than Cohort 2. If safety concerns are identified in the Cohort 1 participants, an interim dose Cohort 1a may be initiated prior to proceeding to Cohort 2 dosing.

Cohort 1 will include up to approximately 5 participants who will receive a tildacerfont dose that is equivalent to the adult dose of 50 mg. Data from the first 2 participants will be considered sentinel and will inform a safety review by an independent DMC. After reviewing the first 2 weeks of data from the sentinel participants, the DMC will make one of three recommendations regarding continuing enrollment:

- 1) If data suggest the dose was well-tolerated by the sentinel participants, Cohort 2 (200 mg equivalent) will be initiated.
- 2) If a safety concern is identified, for example, a sentinel participant experiences an individual stopping criterion or a suspected unexpected serious adverse reaction (SUSAR), the DMC may withhold their recommendation until additional safety data are available from the additional 3 participants in Cohort 1.
- 3) The DMC may also recommend initiating an interim cohort (Cohort 1a) of up to 5 participants to evaluate the same or a different dose (e.g., 50 or 100 mg adult equivalent) before proceeding to Cohort 2 (200 mg equivalent). After reviewing 2 weeks of safety data from Cohort 1a sentinel participants (i.e., first 2 participants), the DMC may recommend initiating Cohort 2. However, if safety concerns are identified, the DMC may recommend reviewing safety data from an additional 3 patients prior to recommending/not recommending initiation of Cohort 2. The DMC will review safety data from Cohort 1a participants and recommend a dose increase to Cohort 2, or initiation of Cohort 3 at the dose used in Cohort 1a.

Cohort 2 will receive the equivalent of the adult dose of 200 mg. Cohort 2 may enroll up to approximately 5 participants. This allows for up to approximately 10 planned participants in the 11- to 17-year-old age group across Cohorts 1, and 2, and up to approximately 15 participants if Cohort 1a is initiated.

Following DMC review of safety data from the first 2 weeks for sentinel participants in Cohort 2 (or Cohort 1a, if utilized), Cohort 3 may be initiated. Cohort 3 will dose no higher than the highest dose found to be safe in 11-to 17-year-olds but enroll up to approximately 10 participants in the younger age group of 2 to 10 years. There will be a DMC review of data from Cohort 3 regarding the initiation of further cohorts with BID dosing ([Table 1](#), [Figure 1](#)).

Cohorts 4 to 9:

All participants in Cohorts 4 to 9 will be enrolled for a 4-week study period. Before escalating to the next highest dose cohort, the DMC will evaluate a total of 4 sentinel participants from the combined cohorts (to initiate a new dosing regimen in a pediatric cohort, data from at least 2 pediatric sentinels must be included in the review).

The study will last approximately 10 weeks including a 2-week Screening Period, a 4-week Treatment Period and a Safety Follow-up visit 30 days after the last dose of study drug). Participants may continue in an extension period upon completion of the 4-week Treatment Period. If participants enroll in the extension after the 4-week Treatment Period, the Safety Follow-up Visit will occur 30 days after the last dose in the extension. Cohorts 4 and 5 will include adults aged ≥ 18 years (up to approximately 5 participants in Cohort 4 and 10 participants in Cohort 5). The 10 participants that may be evaluated in Cohort 5 is to allow for the possibility of more than one dose tested (i.e., 300mg or 400mg BID – per DMC recommendation). Cohorts 6 and 8 will include children ages 11 to 17 years old (up to approximately 5 participants in each cohort) and Cohorts 7 and 9 will include children ages 2 to 10 years old (up to approximately 5 participants in each cohort). Cohorts 8 and 9 may include approximately 5 additional participants each if more than one dose is tested (i.e., 300mg and 400mg equivalent BID). For example, if 5 children are treated with 300mg BID in Cohort 8, the DMC may review safety data from all 5 after 4 weeks of treatment and make a recommendation regarding enrolling another approximately 5 children at 400mg BID ([Table 1](#), [Figure 2](#)).

SPR001-205

Spruce Biosciences, Inc.

CLINICAL STUDY PROTOCOL

Version 5.0

Cohorts 4 and 6 will begin simultaneously with a dose of 200 mg BID in participants aged ≥ 18 years and 200 mg adult equivalent BID in participants aged 11-17 years (200 mg BID has been previously evaluated in adults in study SPR001-202).

The DMC will convene once 4 weeks of safety data is available for 4 sentinels from Cohorts 4 and 6 combined. After reviewing data from these 4 participants (in addition to all other available safety data), the DMC will make a recommendation regarding initiation of Cohorts 5 and 7.

Cohort 5 will enroll adult participants at 300 or 400mg BID (per DMC recommendation) and will provide safety data in adults to support the administration of higher BID doses (i.e., up to 400mg BID) in children and adolescents. Cohort 7 may begin simultaneously with Cohort 5 and will enroll children aged 2-10 years at a dose of 200mg adult equivalent BID.

Once safety data are available for Cohort 5 and 7 sentinels, the DMC will convene and make a recommendation regarding initiation of pediatric cohorts at doses >200 mg BID. The Sponsor will then decide whether to initiate Cohort 8 at a dose up to 400mg BID. Subsequently, the DMC may review data from 4 sentinels from Cohort 8 and make a recommendation regarding further dose increase in the younger age group. Sponsor may then decide whether to initiate Cohort 9 at a dose up to 400mg BID.

A sparse serial blood sampling approach for PK will also be used in Cohorts 4 to 9 on Day 1 (Visit 2) and Week 2/Day 14 (Visit 3). Blood samples for tildacerfont concentration should be obtained pre-dose and between 0.5 - 1.5 hours and 3 - 5 hours post dosing. At these visits, participants will dose in clinic with a meal at 8 am (± 1 hour).

All participants in Cohorts 4-9 will receive open-label tildacerfont for the 4-week treatment period, after which they may be offered optional continued treatment if the clinical Investigator believes it is in the participant's best interest. Once enrolled in the extension period, participants may adjust tildacerfont dose up to the highest dose recommended by the DMC per age group at the Investigator's discretion.

Table 1. Study Cohorts

Cohort	Age	Corresponding Adult Dose	Subject Numbers	Treatment Duration
1	11- to 17-years	50 mg QD	5	12 Weeks
1a ^a	11- to 17-years	To be determined based on DMC recommendation (50 or 100 mg QD)	5	
2	11- to 17-years	200 mg QD	5	
3	2- to 10-years	50 mg QD, 100 mg QD, OR 200 mg QD	10	
4	≥ 18 -years	200 mg BID	5	4 weeks
5	≥ 18 -years	300 and/or 400 mg BID	5+5 ^c	
6	11- to 17-years	200 mg BID	5	
8 ^b	11- to 17-years	300 and/or 400 mg BID	5+5 ^c	
7	2- to 10-years	200 mg BID	5	
9 ^b	2- to 10-years	300 and/or 400 mg BID	5+5 ^c	
			Up to 70 subjects total	

Abbreviations: BID=twice daily; DMC=Data Monitoring Committee; QD=once daily.

^a Cohort 1a is an optional interim dose cohort that may be enrolled only if needed per DMC recommendation and Sponsor decision, in the event of a safety concern in participants in Cohort 1.

^b Cohort 8 and 9 are adaptive cohorts that may be enrolled based on emerging safety data and per DMC and Sponsor recommendation/approval.

^c+5 allows for the option of dosing 300mg before or after 400 mg Cohort is initiated if indicated by the DMC

A schema of the study design is presented in [Figure 1](#) for Cohorts 1, 1a, 2, and 3; and in [Figure 2](#) for Cohorts 4, 5, 6, 7, 8, and 9.

Figure 1. Overall Study Design for Cohorts 1, 1a, 2, and 3

Cohort	Age (years)	Corresponding Adult Dose
1	11 to 17	50 mg QD
1a*	11 to 17	To be determined based on DMC recommendation
2	11 to 17	200 mg QD
3	2 to 10	50 mg QD, 100 mg QD, OR 200 mg QD

*Cohort 1a is an optional interim dose cohort that may be enrolled only if needed per DMC recommendation and Sponsor decision, in the event of a safety concern in sentinel participants in Cohort 1.

[figure not shown]
[figure not shown]

Figure 2. Overall Study Design for Cohorts 4, 5, 6, 8, 7, and 9

Note: Any participant enrolled under protocol amendment 3 may be re-consented to protocol amendment 4 and receive the 12-week treatment course; however, because they will have already contributed PK data, they will not be required to have blood draws for tildacerfont concentration on Days 1 and 14 between 0.5 to- 1.5 hours and between 3 to 5 hours post dosing. Additionally, any participant enrolled under amendment 4 (or any other tildacerfont study) may be re-consented and enrolled under protocol amendment 5.

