Cohort 4 (adults) and Cohort 6 (11-17 years) will initiate concurrently at 200mg BID (200 mg BID has been previously evaluated in adults in study SPR001-201). Upon completion of the 4-week dosing on 4 sentinel participants from Cohorts 4 and 6 combined, the DMC will assess safety data and provide recommendations on continued dosing. If the DMC assesses it to be safe to proceed to a higher dose, Cohort 5 (adults) may be initiated at 300mg or 400mg BID and Cohort 7 (2-10 years) may be initiated at 200mg BID. Following the completion of the 4-week dosing periods for Cohorts 5 and 7, the DMC will review safety data from 4 sentinel participants and offer recommendations on whether to proceed to Cohort 8 (11-17 years) and at what dose (300mg or 400mg BID). Following completion of Cohort 8, the DMC will review the safety data from 4 sentinel participants and provide a recommendation on whether to proceed with Cohort 9 and at what dose (300mg or 400mg BID) ([Table 1](#)).

All cohorts including doses above 200 mg BID will be adaptive, so that the determination to initiate a cohort, and at what dose, may be determined by the Sponsor, within the guidelines of the protocol, based on recommendations by an independent Data Monitoring Committee (DMC) and emerging safety and exposure data. Individual and study stopping criteria will further ensure safety of the participants.

Please see [Section 3](#) for details on Study Design and [Section 6](#) for details on stopping criteria.

Study Conduct: There are 7 scheduled visits over approximately 18 weeks for Cohorts 1 to 3; and 5 scheduled visits over approximately 10 weeks for Cohorts 4 to 9. Visits are detailed in the Schedule of Activities. All visits should be performed on site, but alternative arrangements may be used if an on-site visit is not feasible. Adverse events and concomitant medications will be collected at each visit.

Any participant enrolled under protocol amendment 3 may be re-consented to protocol amendment 4 and receive the 12-week treatment course; however, because they will have already contributed PK data, they will not be required to have blood draws for tildacerfont concentration on Days 1 and 14 between 0.5 to- 1.5 hours and between 3 to 5 hours post dosing. Additionally, any participant enrolled under amendment 4 (or any other tildacerfont study) may be re-consented and enrolled under protocol amendment 5.

Please see [Section 3](#) and [Section 10.2](#) for details on Study Conduct.

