3.1.1. Data Monitoring Committee

An independent DMC will review the available data on an ongoing basis throughout the study and before initiating a new cohort. The DMC will be composed of independent reviewers who are not involved in the conduct of the study. The DMC will advise the Sponsor of any trends or safety issues that may impact the study or study participants. In particular, the occurrence of any clinically significant AE (including but not limited to SAEs, AEs leading to study drug discontinuation/study withdrawal, dose-limiting toxicities [DLTs], and adverse events of special interest [AESIs], all considered at least possibly related to study drug) will receive special consideration (see [Section 7.2.5](#)). The Sponsor will make final decisions concerning the continuation, modification, or termination of the trial. The DMC's scope of responsibility, membership, confidentiality, and procedures will be established in a separate DMC charter. Three DMC reviews are planned during and upon completion of Cohorts 1-3. Three additional DMC reviews are planned during Cohorts 4-9. Ad hoc DMC meetings may be called by the Sponsor or the DMC Chair ([Figure 2](#)).

For Cohorts 1-3, the DMC will review safety data from a minimum of 2 sentinel participants for 2 weeks at each meeting. For Cohorts 4-9, the DMC will review safety data from a minimum of 4 sentinel participants at each meeting, but it is not required that 2 come from each cohort. However, to initiate a

new dosing regimen in a pediatric cohort, data from at least 2 pediatric sentinels must be included in the review.

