5.1. Treatment Administration

Participants will be treated with oral tildacerfont QD for 12 weeks (Cohorts 1 to 3) or BID for 4 weeks (Cohorts 4 to 9).

Pediatric age and weight-based tildacerfont dose levels are defined in [Table 2](#). For each dose level, the amount of study drug that a participant will receive will depend on the participant's age and body weight at Screening according to [Table 2](#).

Cohort 1 will be dosed at the equivalent of the adult 50 mg dose. Cohort 2 will receive the equivalent of the adult dose of 200 mg. If needed based on a safety concern in participants in Cohort 1, an interim dose Cohort 1a may be included. Cohort 3 will dose no higher than Cohort 2 (or Cohort 1a) but enroll up to approximately 10 participants in the younger age group of 2- to 10- years.

Cohorts 4, 6, and 7 will dose at the 200 mg adult dose equivalent BID; and Cohort 5, 8 and 9 will dose at up to 400 mg adult dose equivalent twice per day. Based on DMC recommendation and Sponsor decision, taking into account all available safety and exposure data, Cohorts 5, 8 and 9 may be initiated at 300mg adult equivalent BID for approximately 5 participants each, and then another approximately 5 may be enrolled in each at 400mg adult equivalent BID after DMC review.

Table 2. Tildacerfont Dose Levels and Pediatric Weight-Based Dosing

Weight at Screening (kg)	50 mg QD adult equivalent dose	100 mg QD adult equivalent dose	200 mg QD or BID adult equivalent dose	300mg BID adult equivalent dose	400 mg BID adult equivalent dose
Age group: 2- to 5-years					
13 to 14.1	25	50	75	100	150
14.1 to <21.2	25	50	75	100	150
21.2 to <26.1	25	50	100	150	200
26.1 to <31.8	25	75	100	150	200
31.8 to <33.9	25	75	150	150	300
≥33.9	50	100	150	150	300
Age group: 6- to 10-years					
20 to <23.7	25	50	75	100	150
23.7 to <29.9	25	50	100	150	200
29.9 to <35.5	25	75	100	150	200
35.5 to <39.2	25	75	150	200	300
39.2 to <47.5	50	100	150	200	300
≥47.5	50	100	200	300	400
Age group: 11- to 17-years					
26 to <30.5	25	50	75	100	150
30.5 to <39.2	25	50	100	150	200
39.2 to <45.7	25	75	100	150	200
45.7 to <53.4	25	75	150	200	300
53.4 to <61	50	100	150	200	300
≥61	50	100	200	300	400

Abbreviations: QD=once daily.

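### The commitment to test every BID regimen in adults before children is not written into the visible escalation rules above 200 mg BID

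*Protocol*

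**What the plan says.** **The commitment.** The Synopsis (Study Rationale) states that BID regimens are studied in adults ahead of children. Section 1.2.3 repeats this with dosing up to 400 mg BID in view, and relies on the stepwise design to help keep pediatric exposures within those already studied in adults. SAP Section 7 gives the same reason for enrolling up to 15 adults.

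**The escalation rules.** Section 3.1 and Table 1 let Cohort 5 run at 300 mg BID, 400 mg BID or both. Section 1.2.1 makes the adult step from 300 to 400 mg optional. For pediatric doses above 200 mg BID, Section 3.1 says "Once safety data are available for Cohort 5 and 7 sentinels, the DMC will convene", and the Synopsis has the DMC "offer recommendations on whether to proceed to Cohort 8 (11-17 years) and at what dose (300mg or 400mg BID"). Section 3.1 continues: "The Sponsor will then decide whether to initiate Cohort 8 at a dose up to 400mg BID", and later, for ages 2 to 10, "Sponsor may then decide whether to initiate Cohort 9 at a dose up to 400mg BID". Section 5.1 says that, "taking into account all available safety and exposure data, Cohorts 5, 8 and 9 may be initiated at 300mg adult equivalent BID" for about 5 participants each, "and then another approximately 5 may be enrolled in each at 400mg adult equivalent BID after DMC review". Section 1.2.1 requires a DMC review of 5 participants before a pediatric step to 400 mg and does not mention adult data at 400 mg.

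**The sentinel rule for Cohorts 4 to 9.** Section 3.1.1 asks for "a minimum of 4 sentinel participants at each meeting, but it is not required that 2 come from each cohort". Section 3.1 adds: "to initiate a new dosing regimen in a pediatric cohort, data from at least 2 pediatric sentinels must be included in the review".

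**A cap that is written.** For Cohort 3, Section 3.1 forbids doses above those of Cohort 2 and above the highest dose found safe in adolescents.

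**The concern.** Safety is the primary objective, and prior adult experience is the stated support for taking children to 400 mg equivalent BID. The rules secure the order of cohorts, since adults in Cohort 5 are reviewed before Cohort 8 opens, but they do not secure a match of dose. If Cohort 5 stays at 300 mg BID, the later steps can be followed as written and still take children to a regimen that no adult has received. The commitment then depends on the DMC and the Sponsor recalling a sentence in the rationale when they set the dose.

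The extension inherits the gap. Sections 3.1 and 3.1.3 tie extension doses to the highest dose the DMC has recommended for the age group. Section 3.1.3 adds Sponsor approval and safety labs within 2 to 4 weeks, but no adult data.

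**Working it through.** **1. Planned numbers.** The plan has no power calculation. Its total is the sum of the cohort maxima in Table 1, in order of cohort number: 5+5+5+10+5+10+5+5+10+10 = 70, as stated. Adults: 5+10 = 15. The 5+5 in Cohort 5 already has room for an adult 400 mg group.

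**2. Commitment against rules.**

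| Step | Condition in the rules | Adult data at 400 mg BID required? |
|---|---|---|
| Adults, 300 to 400 mg | optional DMC meeting on 5 participants (1.2.1) | step need not occur |
| Opening Cohort 8, up to 400 mg | DMC review of Cohort 5 and 7 sentinels, then Sponsor decision (3.1) | no |
| Opening Cohort 9, up to 400 mg | DMC review of 4 Cohort 8 sentinels, then Sponsor decision (3.1) | no |
| Cohort 8 or 9, 300 to 400 mg | DMC review of 5 participants (1.2.1, 3.1) | no |
| Pediatric extension | highest dose recommended for the age group (3.1, 3.1.3) | no |

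**3. Paths in Table 1.** Cohorts 5 and 8 can each run at 300, 400 or both: 3 x 3 = 9 pairings. Cohort 8 goes above the highest adult dose in 2 of them (adults at 300 only, with Cohort 8 at 400 or at both). This counts table cells. It ignores timing and Cohort 9 and says nothing about likelihood.

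**4. Size of the mismatch.** Table 2 gives adolescents of 61 kg or more the full adult dose: 2 x 400 = 800 mg/day against 2 x 300 = 600 mg/day in adults; 800/600 = 1.33. Let r be pediatric exposure divided by adult exposure at the same adult-equivalent dose, and assume dose-proportional exposure. Children at 400 mg equivalent then have r x 400/300 times the exposure of adults at 300 mg BID, which exceeds 1 only if r is above 0.75. The documents give no value of r, so the values below are assumed.

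| r (assumed) | 0.50 | 0.60 | 0.75 | 0.90 | 1.00 |
|---|---|---|---|---|---|
| Relative to adults at 300 mg BID | 0.67 | 0.80 | 1.00 | 1.20 | 1.33 |

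Section 1.2.3 reports substantially lower exposures in children, which makes the right-hand columns less likely.

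**5. Sentinel count (secondary).** If exactly 4 sentinels come from Cohorts 5 and 7 and at least 2 are pediatric, the numeric rule allows adult/pediatric splits of 0/4, 1/3 or 2/2. The reference to sentinels from both cohorts argues against 0/4. Cohort 7 receives 200 mg equivalent BID, so only Cohort 5 informs doses above 200 mg BID at this review. The chance of seeing at least one event is 1 - (1 - p)^n; the rates p are assumed, as the documents give none.

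| Adults | p = 10% | p = 20% | p = 30% |
|---|---|---|---|
| 1 | 10% | 20% | 30% |
| 2 | 19% | 36% | 51% |
| 5 | 41% | 67% | 83% |

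**The case against.** The strongest reply is that the protocol already forbids the path. The Synopsis and Section 1.2.1 confine the Sponsor's choice of cohort and dose to the protocol's guidelines, and those include the adults-first statements. A reader might infer from Section 3.1 that the protocol permits 400 mg equivalent BID in children after only 300 mg BID in adults. The documents do not support that reading: such dosing would breach the Synopsis and Section 1.2.3. What stands is narrower. The rules that staff and the DMC would follow do not contain the restriction.

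The DMC is a real safeguard. Section 9.4.4 has it approving cohort progression, and Table 1 footnote b makes Cohorts 8 and 9 depend on DMC and Sponsor approval. Section 6.1.8 stops a cohort or reduces its dose once 2 participants meet stopping criteria. Even so, Sections 1.2.1 and 3.1.1 leave the final decision to the Sponsor, and none of these provisions names a matching adult dose. Earlier adult experience reached 1000 mg QD, but for 2 weeks and on a different regimen.

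A reader might also infer that one adult is enough to open Cohort 8. The numeric rule alone would allow it, but the Synopsis and SAP Section 5 place that review after the 4-week dosing periods of Cohorts 5 and 7. This can be read as requiring completed Cohort 5 dosing, about 5 adults. Four sentinels is also a floor, and the DMC reviews the data available.

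**Conclusion.** The point holds as an internal gap: a regimen-level commitment appears in the Synopsis, Section 1.2.3 and SAP Section 7, and the visible rules in Sections 1.2.1, 3.1 and 3.1.1 do not deliver it above 200 mg BID. It should be fixed, because it concerns the primary objective and the remedy is wording. Confidence is moderate, since Figure 2 and the DMC charter were not available and either could hold the limit.

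The gap is 33% in nominal dose on the affected path. It would be tempting to conclude that children would be exposed above the adult range. The documents do not show this: it would need r above 0.75 under dose proportionality, and reported pediatric exposures are lower than adult ones by an amount not given.

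The missing adult minimum is a smaller point. Its weight depends on how the Synopsis timing is read and on assumed event rates, and the right number is a judgement.

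**What to change.** **Main change.** State in Section 3.1, and align Sections 1.2.1, 3.1.1 and 3.1.3, that doses in Cohorts 8 and 9, steps within them, and pediatric extension doses will not exceed the highest BID dose given for 4 weeks in Cohort 5 and cleared by the DMC. The Cohort 3 cap supplies the form. If Figure 2 or the DMC charter already contains this limit, bring the text into line with it.

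**Secondary change.** Confirm that the review before Cohort 8 requires completed Cohort 5 dosing, or state a minimum number of adults. Two would match the pediatric minimum; five would detect more but take longer. The number is for the Sponsor and the DMC to settle.

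**Cost.** Protocol and charter wording, with no participants beyond the 5 to 10 adults planned for Cohort 5. If adults start at 300 mg BID, a pediatric 400 mg group waits about 6 weeks (2 of screening plus 4 of treatment), plus enrolment and DMC time. The stated commitment already implies that wait, and it does not arise if Cohort 5 opens at 400 mg BID. An adult minimum could delay Cohort 8 if Cohort 5 enrols slowly.

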3.1.3. Extension Period

Participants who complete the 12- or 4-week treatment period, depending on cohort, may be eligible to continue dosing to complete 2 years on treatment in an extension study. Participants will sign a separate informed consent form at Week 12 or Week 4. Pending DMC review, participants in Cohorts 1 and 1a (if indicated) will receive the adult equivalent dose of 200 mg QD during the extension (i.e., Cohort 1 participants will immediately switch to 200 mg equivalent if the DMC has already recommended this dose for Cohort 2, or participants may enter the extension period on 50 mg equivalent and increase to 200 mg equivalent after such a recommendation is made). If a Cohort 1-3 participant is to dose escalate to the 200 mg equivalent, they may do so at the next scheduled visit or come to the clinic for an unscheduled visit and pick up their new supply of study drug. Participants will receive a follow-up phone call 2 weeks after dose escalation to check for AEs.

Further tildacerfont dose adjustments may occur during the extension on a case-by-case basis at the discretion of the Investigator with Sponsor approval. Any extension participant may receive the highest dose recommended by the DMC for their age group. Dose changes (increase or decrease) may occur at a scheduled visit, an unscheduled visit, or via a phone visit, but any dose escalation > 200mg QD will be followed by safety labs (link to list) within 2-4 weeks of the change. Once all participants are in the extension period, safety- data will be reviewed every 6 months by the DMC. Weight-based dose adjustments may be made at any extension visit, with no follow-up labs required.

For Cohorts 1-3, the first visit of the extension will be Week 12. For Cohorts 4-9, Week 4 will be the first extension visit, followed by extension clinic visits at Weeks 8 and 12 (\pm 2 weeks). Starting at Week 12, all participants will attend clinic visits every 12 weeks (\pm 2 weeks).

Approximately a 12-week supply of study drug, as appropriate, will be dispensed at each visit. Approximately 30 days after the last dose of study drug, participants will have a final follow-up visit conducted by telephone. Concomitant medications and AEs will be reviewed. If any ongoing safety issues are identified, the participant may be asked to visit the clinic for additional tests, labs, or assessments.

The extension study visits will include the following:

- Review concomitant medications for any changes

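### Children in the extension could move to a new twice-daily dose before any sentinel of their age at that dose has been reviewed

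*Protocol*

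**What the plan says.** Section 3.1 (Cohorts 4 to 9) states that in the extension "participants may adjust tildacerfont dose up to the highest dose recommended by the DMC per age group", at the Investigator's discretion. Section 3.1.3 applies the ceiling to every cohort: "Any extension participant may receive the highest dose recommended by the DMC for their age group". It adds an approval step that Section 3.1 does not mention: "Further tildacerfont dose adjustments may occur during the extension on a case-by-case basis at the discretion of the Investigator with Sponsor approval".

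Section 3.1.3 also shows what a recommendation means in practice for the once-daily cohorts: "Cohort 1 participants will immediately switch to 200 mg equivalent if the DMC has already recommended this dose for Cohort 2".

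Three provisions bear on oversight. After the change, "any dose escalation > 200mg QD will be followed by safety labs", due within 2 to 4 weeks. On periodic review, "Once all participants are in the extension period, safety- data will be reviewed every 6 months by the DMC". Section 3.1.1 says "Three additional DMC reviews are planned during Cohorts 4-9" and, for starting a new regimen in a pediatric cohort, "data from at least 2 pediatric sentinels must be included in the review". It does not say which age group or dose those pediatric sentinels must come from.

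The SAP does not fill the gap. Its Section 5 repeats the cohort sequence, and its Section 4 leaves the extension analysis to a separate plan.

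**The concern.** Section 1.2.1 staggers the cohorts by age as well as by dose, for caution, and each new dose starts in about 5 participants per age group. That staging protects less if other children of the same age may take the same dose in the extension from the day the cohort opens.

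Those children would also be watched less closely. Under Appendix 3, cohort participants take the first dose in clinic with an hour's observation, have serial samples on Day 1 and at Week 2 (which may be declined in the youngest), a Week 2 ECG, and visits at Weeks 2 and 4. Under Section 3.1.3 an extension participant may change dose by telephone, has laboratory tests 2 to 4 weeks later and, from Week 12, attends clinic every 12 weeks.

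Data from another age group substitute only in part. Section 1.2.3 reports that the PBPK model overestimated exposure in children and that exposure varied with age in Cohorts 1-3. Its wording leaves the direction among children unclear: it describes an inverse relation of exposure to age, then explains it by faster elimination in early childhood, which would point the other way.

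**Working it through.** **1. The plan's own total.** Table 1 cohort sizes for Cohorts 1, 1a, 2, 3, 4, 5, 6, 7, 8, 9: 5 + 5 + 5 + 10 + 5 + 10 + 5 + 5 + 10 + 10 = 70. This reproduces the stated maximum, so the same sizes are used below.

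**2. What each DMC recommendation rests on** (Sections 1.2.1 and 3.1).

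| Data reviewed | Cohort opened | Same age at that dose in the review |
|---|---|---|
| 4 sentinels from Cohort 4 (adults) and Cohort 6 (11-17), 200 mg BID | Cohort 7: ages 2-10, 200 mg BID (with adult Cohort 5) | None aged 2-10 |
| Sentinels from Cohort 5 (adults, 300 or 400 mg BID) and Cohort 7 (ages 2-10, 200 mg BID) | Cohort 8: ages 11-17, 300 or 400 mg BID | None aged 11-17 above 200 mg BID |
| 4 sentinels from Cohort 8 (11-17, 300 or 400 mg BID) | Cohort 9: ages 2-10, 300 or 400 mg BID | None aged 2-10 above 200 mg BID |

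If the opening recommendation sets the extension ceiling, the number of same-age, same-dose sentinels required before extension escalation is 0 in all three rows.

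**3. Reviews available.** Three are planned during Cohorts 4-9 and three openings are described: 3 - 3 = 0 left for Cohort 9 sentinels. Section 1.2.1 describes such a review only if a step from 300 to 400 mg is considered. This is an inference from a count, since ad hoc meetings are allowed.

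**4. Extension children of the same age at each opening.** Upper bounds, assuming planned sizes, everyone continuing and no re-enrolment:

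- Cohort 7: Cohort 3 = 10, and 10/5 = 2 times the new cohort.
- Cohort 8: Cohorts 1, 2, 6 = 5 + 5 + 5 = 15, and 15/5 = 3 times. With Cohort 1a, 15 + 5 = 20, and 20/5 = 4 times.
- Cohort 9: Cohorts 3, 7 = 10 + 5 = 15, and 15/5 = 3 times.

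At a later 300-to-400 mg step the cohort's first 5 could join: 15 + 5 = 20 in each age group (20 + 5 = 25 aged 11-17 with Cohort 1a).

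**5. Re-enrolment.** The note to Figure 2 lets earlier participants enrol under amendment 5. If every BID place were filled from Cohorts 1-3, then 10 - 5 = 5 remain in either age group at each opening (15 - 5 = 10 aged 11-17 with Cohort 1a). Without Cohort 1a the range is 5 to 15.

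**6. Partial uptake.** The documents give no escalation rate. Assuming 25% to 50%: 0.25 × 5 = 1.25 and 0.50 × 5 = 2.5; 0.25 × 15 = 3.75 and 0.50 × 15 = 7.5. That is about 1 to 3 of 5, or 4 to 8 of 15.

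**7. What sentinels would show.** The chance of at least one dose-limiting toxicity in n children is 1 - (1 - p)^n, with p assumed. For n = 4: 18.5%, 34.4% and 59.0% at p = 5%, 10% and 20%. For n = 2: 9.8%, 19.0% and 36.0%. With 0 events in 4, the one-sided 95% upper bound is 1 - 0.05^(1/4) = 52.7%; with 0 in 2 it is 77.6%.

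**The case against.** The strongest reply is that the key step is an inference. Nothing in the available text defines which act of the DMC sets the highest recommended dose for an age group. Its procedures are in a charter that is not available, and Figure 2 is not shown. The once-daily example is a default switch, while later changes are case by case with Sponsor approval, so the analogy is imperfect. This stands as a limit on confidence. But Section 9.4.4 describes the DMC's remit as monitoring safety and approving cohort progression, and no separate release for extension use is mentioned.

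A reader might infer that extension dosing is ungated or that the protocol breaks its own sentinel rule. The documents support neither. The DMC ceiling, Investigator discretion and, in Section 3.1.3, Sponsor approval all apply. The sentinel rule governs opening cohorts and names no age group.

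It can also be said that new enrollees in a cohort start the dose without same-age data, so extension children, who have already completed 4 or 12 weeks on drug, would be held to a stricter standard. That is true, but each new cohort is limited to about 5 closely monitored children, and extension escalators could outnumber them.

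Other safeguards are real. New regimens have been or will be tested in adults first, and pediatric exposures have been substantially lower than adult ones (Section 1.2.3). Individual stopping criteria, ongoing reporting of clinically significant events to the DMC (Sections 6.1.7 and 7.2.5), DMC review by cohort (Section 8.3.4) and ad hoc meetings all apply. None makes escalation wait for same-age data.

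Finally, a handful of sentinels is a weak screen, as step 7 shows. That limits the benefit of the fix, but the present text requires none.

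**Conclusion.** On the natural reading of Sections 3.1 and 3.1.3, same-age extension children could take a new twice-daily dose before any sentinel of that age at that dose has been reviewed. The reading is explicit for 200 mg once daily and inferred for twice-daily doses; a release rule in the charter or Figure 2 would settle it. Confidence is medium.

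The size is an eligible pool of up to 10, 15 and 15 at the opening of Cohorts 7, 8 and 9 (20 at Cohort 8 with Cohort 1a), falling to 5 with full re-enrolment, against about 5 in the new cohort. It would be wrong to infer that this many will escalate: the upper figures assume full uptake, retention and approval. Nor are planned sizes a hard ceiling, since Section 1.2.3 reports 30 children in Cohorts 1-3 against 20 to 25 planned, with no age split or extension entry.

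This is a safety safeguard worth adding because it is cheap. It is not a flaw that undermines the trial.

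**What to change.** In Sections 3.1 and 3.1.3, for doses above 200 mg once daily:

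- Participants may continue in the extension on the dose assigned in their own cohort.
- They may go above it, at the Investigator's discretion and with Sponsor approval in both sections, only to a dose that the DMC has released for extension use in that age group after reviewing 4-week safety data from that age group's sentinels at that dose. State how many sentinels are needed.
- A change of weight band at the same adult-equivalent dose is not an escalation.

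Cohort 7 and Cohort 8 sentinel data already go to planned DMC reviews, so the release decision can be made there. For Cohort 9, use an ad hoc or added review.

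In Section 6.1.8, state that stopping-criterion events in escalated extension participants count toward the 2-participant rule at the age group and dose they are taking. The rule now counts within a cohort and does not say where such a child belongs. Align SAP Section 5.3.1.8, which repeats it. If the charter already contains a release rule, citing it in Sections 3.1 and 3.1.3 would settle the escalation point.

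The cost is wording in the protocol and charter, possibly one more DMC review (3 planned becomes 4), and a wait of some weeks for extension participants seeking a higher dose. Nobody steps down from an assigned dose. Whether the extension schedules should include an ECG is a separate question and not part of this change.
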